## 5.8 Protocol Deviations

Protocol deviations as obtained from a clinical trial management system (CTMS) will be assessed throughout the study. All identified deviations will be reported in the CTMS. Protocol deviations from the CTMS will be provided as part of the CTMS transfer to Biostatistics. Protocol deviations will be summarized for the ITT Population and all protocol deviations will be listed.

# 6. EFFICACY ANALYSES

All efficacy analyses will be based on the ITT Population and PP Population and be displayed in tables side by side for these two populations. The PP Population will be used for sensitivity analysis purpose. Unless stated otherwise, the baseline for all efficacy analyses will be as defined in [Section 11.2](#).

All efficacy analyses will be descriptive only and there will be no statistical testing.

Document: T:\PROJ\Shire\UYA25606\_Biostatistics\Documentation\SAP\SAP\SHP633-306\_SAP\_Final  
v2.0\_20180415.docx

Author: 

Version Number:  
Version Date:

Final V2.0  
15Apr2019

## 6.1 Analyses of Efficacy Endpoints

The efficacy endpoints are the following:

- Absolute and relative change from baseline in weekly PN/IV volume by visit and at EOT.
- Percentage of subjects who achieve at least 20% reduction from baseline in weekly PN/IV volume at both Weeks 20 and 24.
- Percentage of subjects who achieve at least a 20% reduction from baseline in weekly PN/IV volume at each visit
- Change in days per week of PN/IV support from baseline by visit.
- Change in plasma citrulline from baseline by visit.
- Number of subjects who were able to completely wean off of PN/IV support.

Analyses on weekly PN/IV support are based on two data sources: the subject diary data and the investigator prescribed data.

The diary weekly PN/IV volume will be calculated based on the daily volumes recorded in subjects' diaries within 14 days prior to each scheduled visit. The calculation will follow the formula below.

Weekly volume = (sum of daily volumes in the diary/number of days with values) \*7

Missing daily PN/IV volumes will not be imputed. A maximum of 5 missing days (or at least 9 days of non-missing data) from the 14-day intervals are allowable, otherwise the interval will be classified as missing. One exception to this rule is the baseline interval, which will be filtered back up to 28 days prior to first dose until 9 data points are obtained.

Investigator prescribed data is captured in the PN/IV baseline and PN/IV adjustment in eCRF. Investigator prescribed weekly PN/IV volume reported at each visit will be the most recent PN/IV prescription (from either baseline or prescription adjustments) prior to or on the date of visit.

Data will be summarized at all scheduled visits during the 24-week treatment period. An EOT time point will also be added. Therefore,

Document: T:\PROJ\Shire\UYA25606\_Biostatistics\Documentation\SAP\SAP\SHP633-306\_SAP\_Final  
v2.0\_20180415.docx

Author: [REDACTED]

Version Number:  
Version Date:

Final V2.0  
15Apr2019

- PN/IV weekly volume and days per week of PN/IV support will be summarized at Baseline, Weeks 2, 4, 8, 12, 16, 20, 24 and EOT.
- Plasma citrulline will be summarized at Baseline, Weeks 4, 8, 16, 24 and EOT.

Datasets and listings will include data collected at unscheduled visits. Data collected at unscheduled visits will not be included in summaries by timepoint or visit unless specified otherwise.

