## 1. INTRODUCTION

This statistical analysis plan (SAP) provides a technical and detailed elaboration of the statistical analyses of efficacy, safety and pharmacokinetic (PK) data (descriptive summaries only) as described in the final study protocol dated 23 Jan 2018. Specifications for tables, figures, and listings are contained in a separate document. Pharmacokinetics analyses (other than descriptive summaries) will be described in a separate PK SAP.

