### 2.2 Estimand(s)

Absolute change from baseline in weekly PN/IV volume based on diary data at End of Treatment (EOT) in Japanese subjects with PN/IV – dependent SBS in the Intent-to-treat (ITT) Population.

Relative change from baseline in weekly PN/IV volume based on diary data at EOT in Japanese subjects with PN/IV – dependent SBS in the ITT Population.

Number/percentage of subjects who achieved at least 20% decrease from baseline in weekly PN/IV volume based on diary data at Week 20 and Week 24 in Japanese subjects with PN/IV – dependent SBS in the ITT Population.

Number/percentage of subjects who achieved at least 20% decrease from baseline in weekly PN/IV volume based on diary data at Week 20 and Week 24 in Japanese subjects with PN/IV – dependent SBS in the PP Population.

Number/percentage of subjects who achieve at least a 20% reduction from baseline in weekly PN/IV volume based on diary data at each visit in Japanese subjects with PN/IV – dependent SBS in the ITT Population.

Document: T:\PROJ\Shire\UYA25606\_Biostatistics\Documentation\SAP\SAP\SHP633-306\_SAP\_Final  
v2.0\_20180415.docx

Author: [REDACTED]

Version Number:  
Version Date:

Final V2.0  
15Apr2019

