##### 3.1.2 Treatment Period

Following the stabilization period, subjects will enter a 24-week dosing period, during which all subjects will receive teduglutide 0.05 mg/kg subcutaneously (SC) once daily.

Document: T:\PROJ\Shire\UYA25606\_Biostatistics\Documentation\SAP\SAP\SHP633-306\_SAP\_Final  
v2.0\_20180415.docx

Author: [REDACTED]

Version Number:  
Version Date:

Final V2.0  
15Apr2019

At each site visit during the treatment phase, efficacy (adjustments to PN/IV) and safety will be monitored.

Subjects will have blood samples taken for teduglutide PK analysis at predose and 15, 30 minutes and 1, 2, 3, 4, 6, 8, 10, and 12 hours post dose at the baseline visit (Visit 2).

Subjects will also have blood samples taken for teduglutide PK analysis at predose and 1 and 2 hours post dose at Week 4 (Visit 5) or Week 12 (Visit 7) of the treatment period.

All subjects who complete the study may participate in a long-term extension study in which eligible subjects will continue to receive teduglutide.

Schedules of evaluations for the Treatment Period can be found in the protocol.

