#### Binary response to Teduglutide by visit

The number and percentage of subjects who demonstrate a response at each scheduled visit during the 24-week treatment period, as well as EOT, will be presented. A response

Document: T:\PROJ\Shire\UYA25606\_Biostatistics\Documentation\SAP\SAP\SHP633-306\_SAP\_Final  
v2.0\_20180415.docx

Author: [REDACTED]

Version Number:  
Version Date:

Final V2.0  
15Apr2019

is defined as the achievement of at least a 20% reduction from baseline in weekly PN/IV volume.

*Change in days per week of PN/IV support from baseline*

The absolute and percent change in days per week of PN/IV support from baseline to each scheduled visit during the 24-week treatment period, as well as at EOT, will be presented based on diary and investigator prescribed data using descriptive statistics defined in [Section 11.1](#).

*Changes in plasma citrulline from baseline*

The absolute and percent change in plasma citrulline from baseline to each scheduled visit during the 24-week treatment period, as well as at EOT, will be presented using descriptive statistics defined in [Section 11.1](#).

*Number of subjects who are able to completely wean off PN/IV support*

A subject will be considered to have achieved independence from PN/IV (completely weaned off PN/IV) if the investigator prescribes no PN/IV at week 24/EOT and there is no use of PN/IV recorded in the subject diary during the 2 weeks prior to the last dosing visit.

The number and percentage of subjects who completely wean off PN/IV support by Week 24/EOT will be presented. There will be a listing of those who completely weaned off PN/IV.

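### Must SAP 6.1 say whether a PN/IV prescription change is dated by the order or by the first infusion?

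*SAP*

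**What the plan says.** SAP v2.0, section 6.1, states that "Analyses on weekly PN/IV support are based on two data sources: the subject diary data and the investigator prescribed data". The two are built differently.

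- **Diary.** Daily volumes from subjects' "diaries within 14 days prior to each scheduled visit" are averaged and scaled to seven days.
- **Prescribed.** "Investigator prescribed data is captured in the PN/IV baseline and PN/IV adjustment in eCRF". The value at a visit is "the most recent PN/IV prescription (from either baseline or prescription adjustments) prior to or on the date of visit".

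Change in days per week is to be "presented based on diary and investigator prescribed data". The two response paragraphs in 6.1 name no source. Section 2.2 does: it ties every estimand to the diary, for example "Number/percentage of subjects who achieve at least a 20% reduction from baseline in weekly PN/IV volume based on diary data at each visit". Section 1 adds that "Specifications for tables, figures, and listings are contained in a separate document".

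On timing, SAP 3.1.2 says "At each site visit during the treatment phase, efficacy (adjustments to PN/IV) and safety will be monitored". Protocol Amendment 1, Appendix 3, lists reduction attempts at Weeks 2, 4, 8, 12, 16 and 20, each targeted at 10% to 30% of baseline volume, and its Table A1 also provides for increases. Protocol 7.2.2.2 counts the interim safety visit from the day an adjustment takes effect, so ordering and implementing a change can be separate events.

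**The concern.** Adjustments are made at the same visits at which PN/IV volume is summarised. A step ordered at the Week 8 visit and first infused the next day belongs to Week 8 if dated by the order, but first appears at Week 12 if dated by the infusion. SAP 6.1 does not choose, so two programmers could in principle produce different prescribed values for the same subject and visit. The sentence also names weekly volume only, although prescribed days per week is analysed by visit too.

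With about 5 subjects, and individual changes presented, readers will compare the two sources visit by visit. A timing difference could be read as a subject infusing something other than what was prescribed. If response were also tabulated from prescribed data, the choice of date could decide whether a subject counts as a responder at Week 20.

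**Working it through.** There is no power or sample-size figure to reproduce: SAP 3.4 says 5 subjects were chosen without statistical estimation, and all efficacy analyses are descriptive.

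**Inputs.** Step S of 10% to 30% of baseline (Protocol Appendix 3); n = 5 (SAP 3.4); 14-day diary window (SAP 6.1); response threshold of 20% (SAP 6.1). The lag from order to first infusion is not given and is assumed to be 0, 1 or 3 days.

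**1. Effect of the dating rule on one visit.** With a lag of 0 days, both dates fall on the visit day and the readings agree. With a lag of 1 day or more, they differ by S at that visit. For one affected subject the mean moves by S/n: 10/5 = 2 points to 30/5 = 6 points. One prescribed day off for one subject moves mean days per week by 1/5 = 0.2.

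Appendix 3 lets a subject on 2 infusion days be weaned in one step above the 30% limit. Assuming equal volume per infusion day throughout, a subject who began on 4 days would take a last step of 2/4 = 50%, or 50/5 = 10 points. A subject who began on 3 days would first need a 1/3 = 33.3% cut to reach 2 days, which exceeds the limit, so under this assumption 10 points is the largest case.

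**2. Comparison with the diary.** Take cuts of 10% at Weeks 2, 4 and 8, each first infused one day later. Entries are % change from baseline.

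| Visit | Diary | Prescribed, order date | Prescribed, first infusion |
|---|---|---|---|
| Week 2 | 0 | -10 | 0 |
| Week 4 | -9.3 | -20 | -10 |
| Week 8 | -20 | -30 | -20 |

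The Week 4 diary value is 10 × 13/14 = 9.3, because one day of the window precedes the first infusion. Under order dating, prescribed minus diary at an adjustment visit is the whole new step, apart from the 0.7-point window effect at Week 4. An increase reverses the sign: a 20% cut at Week 8 undone at the Week 20 visit gives a prescribed change of 0 against a diary change of -20 at Week 20.

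Naming a date therefore closes the gap only if the date is first infusion and infusion starts after the visit day. Even then, after a Week 2 cut, a Week 4 residual of 10 × 1/14 = 0.7 to 30 × 3/14 = 6.4 points remains for lags of 1 to 3 days. If the named date is the order date, the gap stays. It comes from setting the prescription at the visit against a 14-day look-back, which SAP 6.1 states openly.

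**3. Response at both Weeks 20 and 24, if tabulated from prescribed data.** Let the reduction before Week 20 be 0, 10 or 20%, and the Week 20 step 10, 20 or 30%, either kept or reversed before Week 24.

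- Order date: Week 20 = prior + step.
- Next-day infusion: Week 20 = prior.
- Week 24 = prior + step if kept, prior if reversed, under both.

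The readings disagree in 5 of 9 kept cases (0+20, 0+30, 10+10, 10+20, 10+30) and in 0 of 9 reversed cases. Each affected subject is 1/5 = 20 points of the rate. The grid shows that disagreement is possible; it gives no probability.

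**4. What does not depend on the date.**

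- The SAP 2.2 estimands and the missing-data criterion for the per-protocol set (SAP 4.3) use the diary.
- In every scenario run, prescribed Week 24 values were identical under both readings.
- Weaning also requires no diary use in the preceding 2 weeks, so a same-day order cannot by itself create a weaned subject.

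**The case for a change.** The best argument for a change is that Protocol 9.3 assigns definitions to the SAP, the SAP chose to report both sources, and one sentence naming the date would make the prescribed tables reproducible from the SAP alone. It could also extend the rule to days per week and repeat the diary as the source for response.

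The omission is real: neither SAP 6.1 nor Protocol 7.2.2.2 names the date field. The consequence is less secure. Divergent programming needs an eCRF with two usable dates, and nothing in the documents shows that it has them. The eCRF instructions and table specifications were not available and may settle the matter. A sentence recording whichever date the eCRF collects would leave the derivation as it is. The ordinary reading of a prescription in force by the visit is the prescription's own date; infused volume is what the diary measures.

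The other additions are largely covered. Protocol 7.2.2.2 records prescribed volume and days together, so selecting the latest prescription selects both. SAP 6.1 already states both time rules, and SAP 2.2 already assigns response to the diary.

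**Conclusion.** No change to the plan is needed. SAP 6.1 leaves the adjustment date unnamed, and if infusion starts after the visit day the two readings of a prescribed value at Weeks 2 to 20 differ by one step. For one subject of 5 that is normally 2 to 6 points on the mean, or 10 points in the largest weaning case under the equal-volume assumption. The 20-point responder effect would need a prescribed-source response table, order dating and a kept Week 20 step. No diary-based estimand is affected and no hypothesis is tested.

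Two limits apply. The Week 24 result rests on Appendix 3 listing no reduction attempt then. Table A1 allows increases at scheduled visits, so a prescription changed on the Week 24 day would be an exception. For a subject who stops early, the prescribed EOT value (SAP 11.4) could include a same-day change. Treating the prescribed tables as supportive is an inference from SAP 2.2, since 6.1 does not rank the sources.

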#### Change in weekly PN/IV volume from baseline

The absolute and percent change in weekly PN/IV volume from baseline to each scheduled visit during the 24-week treatment period, as well as at EOT, will be presented using the descriptive statistics defined in [Section 11.1](#).

Percent change in weekly PN/IV volume from baseline at each scheduled visit will be calculated using the formula below:

% change in weekly PN/IV volume at the visit = [(weekly PN/IV volume at the visit – weekly PN/IV volume at baseline) / weekly PN/IV volume at baseline] \* 100

95% confidence intervals of the mean will be generated for Week 24 and EOT.

Mean  $\pm$  SE plots of absolute and percent change from baseline in weekly PN/IV volume will be generated. In addition, individual absolute and percent change from baseline in weekly PN/IV volume will be presented for each subject.

#### Response to Teduglutide at both Weeks 20 and 24

The number and percentage of subjects who demonstrate a response at Week 20 and again at Week 24 will be presented. A response is defined as the achievement of at least a 20% reduction from baseline in weekly PN/IV volume.

#### Binary response to Teduglutide by visit

The number and percentage of subjects who demonstrate a response at each scheduled visit during the 24-week treatment period, as well as EOT, will be presented. A response

Document: T:\PROJ\Shire\UYA25606\_Biostatistics\Documentation\SAP\SAP\SHP633-306\_SAP\_Final  
v2.0\_20180415.docx

Author: [REDACTED]

Version Number:  
Version Date:

Final V2.0  
15Apr2019

is defined as the achievement of at least a 20% reduction from baseline in weekly PN/IV volume.

*Change in days per week of PN/IV support from baseline*

The absolute and percent change in days per week of PN/IV support from baseline to each scheduled visit during the 24-week treatment period, as well as at EOT, will be presented based on diary and investigator prescribed data using descriptive statistics defined in [Section 11.1](#).

*Changes in plasma citrulline from baseline*

The absolute and percent change in plasma citrulline from baseline to each scheduled visit during the 24-week treatment period, as well as at EOT, will be presented using descriptive statistics defined in [Section 11.1](#).

*Number of subjects who are able to completely wean off PN/IV support*

A subject will be considered to have achieved independence from PN/IV (completely weaned off PN/IV) if the investigator prescribes no PN/IV at week 24/EOT and there is no use of PN/IV recorded in the subject diary during the 2 weeks prior to the last dosing visit.

The number and percentage of subjects who completely wean off PN/IV support by Week 24/EOT will be presented. There will be a listing of those who completely weaned off PN/IV.

### **6.1.1 Sensitivity Analyses of Efficacy Endpoint(s)**

The PP Population will be used for sensitivity analysis purpose.

### **6.2 Multiplicity Adjustment**

As there will be no statistical testing given the small sample size, no adjustment for multiple comparisons will be made.

### **6.3 Subgroup Analyses**

No subgroup analysis will be performed.

Document: T:\PROJ\Shire\UYA25606\_Biostatistics\Documentation\SAP\SAP\SHP633-306\_SAP\_Final  
v2.0\_20180415.docx

Author: 

Version Number:

Final V2.0

Version Date:

15Apr2019

## 7. SAFETY ANALYSIS

The safety analysis will be performed using the Safety Population. Safety variables include AEs, clinical laboratory variables, vital signs, ECG variables, physical examination, 48-hour urine output and antibodies to Teduglutide. For each safety variable, the last value collected before the first dose of the investigational product will be used as the baseline for all analyses of that safety variable.

### 7.1 Adverse Events

AEs will be coded using MedDRA. Investigator verbatim as well as PT and SOC will be included in the listings.

Treatment emergent AEs (TEAEs) are defined as AEs whose onset occurs, severity worsens, or intensity increases after receiving the study medication. AEs with an unknown date of onset and a stop date after the start of the study treatment or unknown stop date will be included as TEAEs. Any AE with a start date equal to the date of first dose, where the time of the AE cannot definitively place the start of the AE prior to the first dose, will be considered treatment emergent. If any AE records contain only partial dates, these will be handled by imputation, as described in [Section 11.5.3](#). AEs which are not treatment emergent will be flagged in listings.

AEs will be summarized overall using descriptive statistics (e.g., number and percent of subjects). The number of events will also be presented. Categories summarized will include any TEAEs, severity of TEAEs, investigator assessment of relationship of TEAEs to study treatment, treatment emergent serious AEs (TESAEs), severity of TESAEs, investigator assessment of relationship of TESAEs to study treatment, TEAEs leading to death, and TEAEs leading to study treatment discontinuation.

TEAEs will be summarized using number and percentage of subjects. Subject incidence for AEs within each SOC and PT will be presented, unless otherwise specified. The number of events will also be presented. Categories summarized are as follows:

- TEAEs,
- Severity of TEAEs,
- Investigator assessment of relationship of TEAEs to study treatment,
- TESAEs.

Presentation by SOC and PT will present SOC sorted alphabetically and PT within SOC by descending incidence.

Listings will be provided for serious adverse events (SAEs), AEs leading to death, AEs leading to study treatment discontinuation and AEs leading to study discontinuation. Adverse events leading to study discontinuation are not captured in the AE eCRF page, however primary reason for study discontinuation due to AE is capture in the End of Study eCRF page with the relevant AE number. This data will be used to present the AE leading to study discontinuation. The listings will be sorted by subject identifier and will include SOC, PT, reported term, start date/time, end date/time, frequency, severity, relationship, action taken, and outcome.

For AEs with partial dates, the imputed dates described in [Section 11.5.3](#) will be used to determine the onset interval.

### 7.1.1 Adverse Events of Special Interest

An AE of special interest is an AE (serious or nonserious) of scientific and medical concern specific to the sponsor's product or program and for which ongoing monitoring and immediate notification by the investigator to the sponsor is required.

The AEs of special interest that require expedited regulatory reporting for this study include the following:

- Growth of preexisting polyps of the colon
- Benign neoplasia of the GI tract including the hepatobiliary system
- Tumor-promoting ability (e.g., benign and/or malignant neoplasia of any kind, not limited to those of the GI or hepatobiliary system)

The preferred terms corresponding to each grouping of events of special interest will be identified by Takeda. A listing indicating the MedDRA terms corresponding to each grouping of events of special interest can be found in [Appendix I](#).

For each grouping of events of special interest, PT, the number and percentage of subjects with at least one TEAE of special interest will be presented. The number of events of special interest will also be summarized.

Listing for AE of special interest will also be provided.

Document: T:\PROJ\Shire\UYA25606\_Biostatistics\Documentation\SAP\SAP\SHP633-306\_SAP\_Final  
v2.0\_20180415.docx

Author: 

Version Number:

Final V2.0

Version Date:

15Apr2019

## 7.2 Clinical Laboratory Data

Clinical laboratory tests are to be performed at site visits with results processed by a central laboratory. Laboratory tests include the following ([Table 2](#)):

Document: T:\PROJ\Shire\UYA25606\_Biostatistics\Documentation\SAP\SAP\SHP633-306\_SAP\_Final  
v2.0\_20180415.docx

Author: [REDACTED]

Version Number:  
Version Date:

Final V2.0  
15Apr2019

**Table 2 List of Laboratory Tests**

Hematology:	Biochemistry:

• Hematocrit

• Hemoglobin

• Platelet count

• Red blood cell count

• Red blood cell morphology, if needed

• White blood cell count with differential

	

• Albumin

• Alkaline phosphatase

• Alanine aminotransferase

• Amylase

• Aspartate aminotransferase

• Bilirubin (total, direct and indirect)

• Blood urea nitrogen

• Calcium (total)

• Chloride

• Cholesterol

• Citrulline (plasma)

• C-reactive protein

• Creatinine

• Creatinine clearance

• Gamma-glutamyl transferase

• Glucose

• Lipase

• Magnesium

• Phosphorus

• Potassium

• Sodium

• Triglycerides

• Uric acid

Urinalysis:	

• Blood

• Glucose

• Leucocytes

• Microscopic analysis

• pH

• Protein

• Specific gravity

• Urine Sodium

	

